1. INTRODUCTION

During the course of the study the Investigator will remain vigilant for increases in liver biochemistry. The investigator is responsible for determining whether a patient meets potential Hy's Law (PHL) criteria at any point during the study.

The Investigator participates, together with AstraZeneca clinical project representatives, in review and assessment of cases meeting PHL criteria to agree whether Hy's Law (HL) criteria are met. HL criteria are met if there is no alternative explanation for the elevations in liver biochemistry other than Drug Induced Liver Injury (DILI) caused by the Investigational Medicinal Product (IMP).

The Investigator is responsible for recording data pertaining to PHL/HL cases and for reporting Adverse Events (AE) and Serious Adverse Events (SAE) according to the outcome of the review and assessment in line with standard safety reporting processes.

2. DEFINITIONS

Potential Hy's Law (PHL)

Aspartate Aminotransferase (AST) or Alanine Aminotransferase (ALT) $\geq 3x$ Upper Limit of Normal (ULN) **together with** Total Bilirubin (TBL) $\geq 2x$ ULN at any point during the study following the start of study medication irrespective of an increase in Alkaline Phosphatase (ALP).

Hy's Law (HL)

AST or ALT $\geq 3x$ ULN **together with** TBL $\geq 2x$ ULN, where no other reason, other than the IMP, can be found to explain the combination of increases, eg, elevated ALP indicating cholestasis, viral hepatitis, another drug.

For PHL and HL the elevation in transaminases must precede or be coincident with (i.e. on the same day) the elevation in TBL, but there is no specified timeframe within which the elevations in transaminases and TBL must occur.

3. IDENTIFICATION OF POTENTIAL HY'S LAW CASES

In order to identify cases of PHL it is important to perform a comprehensive review of laboratory data for any patient who meets any of the following identification criteria in isolation or in combination:

- ALT $\geq 3x$ ULN
- AST $\geq 3x$ ULN
- TBL $\geq 2x$ ULN

When a patient meets any of the identification criteria, in isolation or in combination, the central laboratory will immediately send an alert to the Investigator (also sent to AstraZeneca representative).

The Investigator will also remain vigilant for any local laboratory reports where the identification criteria are met, where this is the case the Investigator will:

- Notify the AstraZeneca representative
- Request a repeat of the test (new blood draw) by the central laboratory
- Complete the appropriate unscheduled laboratory CRF module(s) with the original local laboratory test result

When the identification criteria are met from central or local laboratory results the Investigator will without delay:

- Determine whether the patient meets PHL criteria (see Section 2 of this Appendix for definition) by reviewing laboratory reports from all previous visits (including both central and local laboratory results)

The Investigator will without delay review each new laboratory report and if the identification criteria are met will:

- Notify the AstraZeneca representative
- Determine whether the patient meets PHL criteria (see Section 2 of this Appendix for definition) by reviewing laboratory reports from all previous visits
- Promptly enter the laboratory data into the laboratory CRF

4. FOLLOW-UP

4.1 Potential Hy's Law Criteria not met

If the patient does not meet PHL criteria the Investigator will:

- Inform the AstraZeneca representative that the patient has not met PHL criteria.
- Perform follow-up on subsequent laboratory results according to the guidance provided in the Clinical Study Protocol.

4.2 Potential Hy's Law Criteria met

If the patient does meet PHL criteria the Investigator will:

- Notify the AstraZeneca representative who will then inform the central Study Team

The Study Physician contacts the Investigator, to provide guidance, discuss and agree an approach for the study patients' follow-up and the continuous review of data. Subsequent to this contact the Investigator will:

- Monitor the patient until liver biochemistry parameters and appropriate clinical symptoms and signs return to normal or baseline levels, or as long as medically indicated
- Investigate the etiology of the event and perform diagnostic investigations as discussed with the Study Physician. This includes deciding which of the tests available in the Hy's law lab kit should be used.
- Complete the three Liver CRF Modules as information becomes available
- If at any time (in consultation with the Study Physician) the PHL case meets serious criteria, report it as an SAE using standard reporting procedures

5. REVIEW AND ASSESSMENT OF POTENTIAL HY'S LAW CASES

The instructions in this Section should be followed for all cases where PHL criteria are met.

No later than 3 weeks after the biochemistry abnormality was initially detected, the Study Physician contacts the Investigator in order to review available data and agree on whether there is an alternative explanation for meeting PHL criteria other than DILI caused by the IMP. The AstraZeneca Medical Science Director and Global Safety Physician will also be involved in this review together with other subject matter experts as appropriate.

According to the outcome of the review and assessment, the Investigator will follow the instructions below.

If there is an agreed alternative explanation for the ALT or AST and TBL elevations, a determination of whether the alternative explanation is an AE will be made and subsequently whether the AE meets the criteria for a SAE:

- If the alternative explanation is **not** an AE, record the alternative explanation on the appropriate CRF
- If the alternative explanation is an AE/SAE, record the AE /SAE in the CRF accordingly and follow the AZ standard processes

If it is agreed that there is **no** explanation that would explain the ALT or AST and TBL elevations other than the IMP:

- Report an SAE (report term ‘Hy’s Law’) according to AstraZeneca standard processes.
 - The ‘Medically Important’ serious criterion should be used if no other serious criteria apply
 - As there is no alternative explanation for the HL case, a causality assessment of ‘related’ should be assigned.

If, there is an unavoidable delay, of over 3 weeks, in obtaining the information necessary to assess whether or not the case meets the criteria for HL, then it is assumed that there is no alternative explanation until such time as an informed decision can be made:

- Report an SAE (report term ‘Potential Hy’s Law’) applying serious criteria and causality assessment as per above
- Continue follow-up and review according to agreed plan. Once the necessary supplementary information is obtained, repeat the review and assessment to determine whether HL criteria are met. Update the SAE report according to the outcome of the review

Clinical Study Protocol Appendix D
Drug Substance EXENATIDE
Study Code D5551C00002
Edition Number Version 01 Amendment 03
Date 09 April 2015

Appendix E
Extended Safety Follow-Up Period

1. Overview and Rationale

In response to a request from the European Medicines Agency Committee, patients participating in Study BCB114 will be observed in an Extended Safety Follow-Up Period following discontinuation of study medication administration. Long-term follow-up of pediatric patients participating in Study BCB114 will allow observation of ongoing development and growth on an individual patient basis and a description of the occurrence of selected adverse events in pediatric patients in the absence of EQW treatment following up to 52 weeks of EQW administration.

2. Objective

The objectives of this Extended Safety Follow-Up Period are:

- To describe safety parameters over time following discontinuation of study medication administration, including the following:
 - Adverse events (AEs) of special interest
 - Ongoing prescription medications
 - Height and weight
 - Tanner pubertal stage
 - Carcinoembryonic antigen (CEA) concentration
 - Calcitonin concentration

3. Study Design

Following discontinuation of study medication administration, patients with a height increase of at least 5 mm between Visit 8 (Week 28) and Visit 11 (Week 62/Study Termination) will enter the Extended Safety Follow-Up Period. Patients who discontinue study medication administration prior to Visit 10 (Week 52/Study Termination) will also enter the Extended Safety Follow-Up Period, unless they have a height increase of less than 5 mm over a 6-month interval at study-site visits prior to discontinuation of study medication. Patients who do not have height assessments at study-site visits over a 6-month interval prior to discontinuation of study medication will enter the Extended Safety Follow-Up Period.

During the Extended Safety Follow-Up Period, patients will return to the study site at approximately 6-month intervals for a period of up to 3 years or until the difference between 2 height measurements over a 6-month interval is less than a 5 mm increase (whichever comes first). During the Extended Safety Follow-Up period, adverse events of special interest (AESIs) (see [Table 1](#)), and ongoing prescription medication will be reviewed, height, weight, and Tanner pubertal stage will be assessed, and CEA and calcitonin concentrations will be measured.

4. Visit Structure

The Extended Safety Follow-Up Period will include up to 6 study-site visits (6-month intervals for a period of up to 36 months). The first visit during the Extended Safety Follow-Up Period is to occur 6 months after discontinuation of study medication administration or 6 months after Visit 10 (Week 52), whichever comes first. Patients will subsequently return to the study site at 6-month intervals (± 2 weeks). Patients will discontinue participation in the Extended Safety Follow-Up period after 3 years or once they have a height increase of less than 5 mm between two 6-month interval visits.

5. Study Duration

The duration of the Extended Safety Follow-Up Period will be a maximum of 3 years.

6. Study Population

Patients who have participated in Study BCB114 who have a height increase of at least 5 mm between Visit 8 (Week 28) and Visit 11 (Week 62/Study Termination) will participate in the Extended Safety Follow-Up Period. Patients who discontinue study medication prior to Visit 10 (Week 52) will also participate in the Extended Safety Follow-Up Period, unless they have a height increase of less than 5 mm over a 6-month interval at study-site visits prior to discontinuation of study medication. Patients who do not have height assessments at study-site visits over a 6-month interval prior to discontinuation of study medication will enter the Extended Safety Follow-Up Period.

Patients participating in the standardized meal test ([Appendix F](#)) will also participate in the Extended Safety Follow-Up Period, with no changes to the procedures and study site visits associated with [Appendix F](#)

7. Patient Restrictions

There are no patient restrictions for the Extended Safety Follow-Up Period. No fasting or withholding of medications is required prior to Extended Safety Follow-Up Period visits.

8. Restricted Medications

During the Extended Safety Follow-Up Period, patients will be treated at the discretion of their healthcare provider, with no medication restrictions.

9. Study Medications

No study medications will be administered during the Extended Safety Follow-Up Period.

10. Study Methods

During the Extended Safety Follow-Up Period, patients will return to the study site at 6-month intervals.

All patients will undergo the following procedures during each Extended Safety Follow-Up Period visit:

- Review of ongoing prescription medication
- Review of AESIs (see Table 1)
- Assessment of body weight and height
- Assessment of Tanner pubertal stage
- Blood samples will be collected for assessment of:
 - Calcitonin
 - CEA

Patients with an increase in height of 5 mm or greater, compared to a height measurement obtained 6 months previously, will be asked to return for additional safety follow-up visits at 6-month intervals, for a maximum observation period of 3 years or 36 months.

11. Safety Assessments

Assessment of body weight, height, Tanner pubertal stage, calcitonin concentration, and CEA concentration in the Extended Safety Follow-Up Period will be performed as described in the main protocol.

Review of medications during the Extended Safety Follow-Up period will focus on ongoing prescription medications.

Adverse events of special interest (Table 1) will be assessed at all visits during the Extended Safety Follow-Up Period and the eCRF will be completed if it is determined that the patient has experienced one or more of the listed AESIs. Other serious and nonserious AEs will be collected through routine postmarketing spontaneous reporting and according to the relevant medication(s) the patient is receiving (which may or may not include exenatide).

Table 1. List of Adverse Events of Special Interest to be Recorded in CRF

-
- Hematological malignancies
 - Thyroid neoplasms
 - Pancreas neoplasms
 - Aplastic anemia
 - Pancreatitis
 - Pregnancy and pregnancy outcomes (including congenital anomalies)
-

Note: Table to be updated in the case that additional adverse events of special interest are identified.

12. Statistical Considerations

a. Analysis Populations

Safety data will be listed for the **Extended Safety Follow-Up Population**, which will consist of all patients who participate in at least one Extended Safety Follow-Up Period visit.

13. General Considerations

Data collected in the Extended Safety Follow-Up Period is for descriptive purposes and is not associated with a predefined hypothesis or test. Data will be listed by individual patient. Missing data will not be imputed. No descriptive summaries will be prepared. In addition, data collected throughout the treatment period and the Extended Safety Follow-Up Period will be listed for each individual patient in the Extended Safety Follow-Up Population in individual patient profiles.

Clinical Study Protocol Appendix F

Drug Substance	EXENATIDE
Study Code	D5551C00002
Edition Number	2
Date	14 December 2017

Appendix F
Mixed Meal Substudy

Clinical Study Protocol Appendix F
Drug Substance EXENATIDE
Study Code D5551C00002
Edition Number 2
Date 14 December 2017

1. PURPOSE

The purpose of this exploratory substudy is to evaluate the change in postprandial beta-cell function after approximately 28 weeks of exenatide once weekly therapy and at approximately 10 to 12 weeks following cessation of drug therapy.

2. SCOPE

A standardized mixed-meal test will be implemented prior to treatment at baseline Visit 2 (Week 0), Visit 10 (Week 52), and at Visit 11 (Week 62) (approximately 10 to 12 weeks following Visit 10 (Week 52) in a subset of subjects enrolled in Protocol BCB114.

The standardized mixed-meal test will be conducted in approximately 20 subjects at a number of sites participating in Protocol BCB114. As all subjects who remain in the trial will receive at least 28 weeks of treatment with exenatide once weekly, subjects from either treatment arm (exenatide once weekly or placebo) are eligible to participate in the addendum. At the time of the first post-baseline assessment (Visit 10 (Week 52), subjects participating in the addendum will have been exposed to exenatide once weekly for at least 28 weeks.

3. BACKGROUND AND RATIONALE

Exenatide improves glycemic control in subjects with type 2 diabetes mellitus, enhances glucose-dependent insulin secretion by the pancreatic beta cell, suppresses inappropriately elevated glucagon secretion during periods of hyperglycemia, and slows gastric emptying.

Several clinical studies have shown that exenatide reduces fasting and postprandial glucose concentrations through mechanisms of actions including glucose-dependent suppression of glucagon secretion¹⁻², slowed gastric emptying and enhanced splanchnic glucose uptake, resulting in slowed appearance of meal-derived glucose in the circulation¹⁻², and effects on the beta-cell including the enhancement of glucose-dependent insulin secretion^{1,3} and the restoration of first-phase insulin secretion.⁴

Diminished first-phase insulin secretion is an early pathophysiologic feature of type 2 diabetes, and plays a key role in sustained postmeal hyperglycemia. A number of different beta-cell markers suggest that exenatide treatment is associated with improvements in both first--and second-phase insulin secretion in subjects with type 2 diabetes.⁴

This substudy is designed to assess postprandial beta-cell function specifically evaluating potential restoration of the beta-cell response following approximately 28 weeks of exenatide once weekly treatment and at approximately 10 to 12 weeks following cessation of drug therapy.

4. OBJECTIVES

The primary objective of this exploratory substudy is:

- To evaluate the effect of exenatide once weekly on postprandial beta-cell function as assessed by C-peptide secretion during a mixed-meal test, following approximately 28 weeks of exenatide once weekly treatment and at approximately 10 to 12 weeks following cessation of drug therapy.

The secondary objective of this exploratory substudy is:

- To assess postprandial glucose and glucagon responses during a mixed-meal test following approximately 28 weeks of exenatide once weekly treatment and at approximately 10 to 12 weeks following cessation of drug therapy.

5. STUDY DESIGN

5.1 Design Description

At baseline Visit 2 (Week 0), the study procedures to be assessed are outlined in the main protocol and in Section 9.1.1 of this substudy. Study medication will be administered after all study procedures outlined in the main protocol and substudy are completed.

At Visit 10 (Week 52), the study procedures to be assessed are outlined in the main protocol and in Section 9.1.2 of this addendum.

10 to 12 weeks following the discontinuation of study medication administration, subjects will return to the study site for Visit 11 (Week 62/Study Termination). At this visit, the study procedures to be assessed are outlined in the main protocol and in addition, subjects will receive the standardized mixed-meal test and have blood drawn for additional postprandial pharmacodynamic assessments for the purpose of the substudy. Substudy procedures to be performed at this visit are outlined in Section 9.1.3.

6. STUDY DURATION

The total duration of the substudy will be approximately 62 weeks; the substudy will be initiated at baseline Visit 2 (Week 0) and concluded at Visit 11 (Week 62/Study Termination), approximately 10 to 12 weeks following the discontinuation of study medication at Visit 10 (Week 52).

7. STUDY POPULATION

Approximately 20 subjects participating in Protocol BCB114 who have volunteered to participate will be included in the substudy.

7.1 Inclusion Criteria

All subjects participating in the substudy should adhere to the inclusion criteria listed in Protocol BCB114.

7.2 Exclusion Criteria

All subjects participating in the substudy should adhere to the exclusion criteria listed in Protocol BCB114.

7.3 Restricted Medications

During the approximately 10 to 12 week off-drug period, substudy subjects should not be treated with:

- Insulin secretagogues (e.g., meglitinide, nateglinide, and sulfonylureas), DPP-4 inhibitors, or GLP-1 receptor agonists (e.g., exenatide and liraglutide)

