4.2 Inclusion criteria

For inclusion in the study patients should fulfil the following criteria:

1. Is a child or an adolescent of 10 to <18 years old, at Visit 1 (Screening)
2. Has been diagnosed with type 2 diabetes mellitus per American Diabetes Association diagnostic criteria
3. HbA1c of 6.5% to 11.0%, inclusive, in patients not taking insulin/SU, and of 6.5% to 12.0%, inclusive, in patients taking insulin/SU, at Visit 1 (Screening)
4. Has a C-peptide of >0.6 ng/mL at Visit 1 (Screening)
5. Has been treated with diet and exercise alone or in combination with a stable dose of an oral antidiabetic agent (eg, metformin and/or SU) and/or insulin for their type 2 diabetes for at least 2 months prior to Visit 1 (Screening)
6. Has a fasting plasma glucose concentration <280 mg/dL (15.5 mmol/L) at Visit 1 (Screening)
7. Either is not treated with or has been on a stable treatment regimen with any of the following medications for a minimum of 1 month prior to Visit 1 (Screening):
 - (a) Oral contraceptives (female patients)
 - (b) Antihypertensive agents
 - (c) Lipid-lowering agents
 - (d) Thyroid replacement therapy
 - (e) Antidepressant agents
8. Is male, or is female and meets all the following criteria:
 - (a) Not breastfeeding
 - (b) Negative serum pregnancy test result (human chorionic gonadotropin, beta subunit [β hCG]) at Visit 1 (Screening)
 - (c) If of childbearing potential, must practice and be willing to continue to practice appropriate birth control (defined as at least 1 method which results in a low failure rate, ie, less than 1% per year, when used consistently and correctly, such as implants, injectables, hormonal contraceptives, some intrauterine contraceptive

- devices, sexual abstinence, tubal ligation or occlusion, or a vasectomized partner) during the entire duration of the study and must not be planning to conceive
9. Has clinical laboratory test values (clinical chemistry, hematology, and urinalysis) judged as not clinically significant by the Investigator at Visit 1 (Screening)
 10. Has physical examination and ECG results deemed not clinically significant by the Investigator at Visit 2 (Week 0)

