 - (c) Inhaled glucocorticoids at a dose equal to or above 1,000 µg Flovent[®] (fluticasone propionate) daily
 - (d) Weight loss medication(s) (including over the counter) within 30 days of Visit 1 (Screening)
 - (e) Alpha-glucosidase inhibitors, meglitinide, nateglinide, or pramlintide for >1 week in the 1 month prior to Visit 1 (Screening)
 - (f) DPP-4 inhibitors within 30 days prior to Visit 1 (Screening).
11. Has admitted use of anabolic steroids within the past 60 days or is planning use during the study

12. Is an immediate family member (spouse, parent, child, or sibling; biological or legally adopted) of personnel directly affiliated with the study at the clinical study site, or is directly affiliated with the study at the clinical study site
13. Is pregnant
14. Is employed by AstraZeneca (ie, an employee, temporary contract worker, or designee responsible for the conduct of the study).

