5.6 Concomitant and post-study treatments

Patients must follow the medication restrictions outlined in the inclusion and exclusion criteria (Section 4.2 and 4.3) during the study. Dosages for certain concomitant medications should be maintained constant during the study (Section 4.2), unless instructed otherwise by the Investigator or a treating physician. For patients on insulin, the dose should be kept constant as far as possible, though modifications of the dose of insulin may have to be made to reduce the risk of hypoglycemia. Any change in regimen for any concomitant medication, including restricted concomitant medications, must be reported to the Sponsor.

Other medication, which is considered necessary for the patient's safety and well being, may be given at the discretion of the Investigator and recorded in the appropriate sections of the Case Report Form (CRF).

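### The mixed-meal substudy admits patients on background sulfonylurea but bars the class in the off-drug period, so in any such patient the descriptive Week 62 C-peptide change mixes lasting EQW effect with loss of sulfonylurea

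*Protocol*

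**What the plan says.** Substudy entry is the main-study entry. Appendix F 7.1 reads "All subjects participating in the substudy should adhere to the inclusion criteria listed in Protocol BCB114", and 7.2 reads "All subjects participating in the substudy should adhere to the exclusion criteria listed in Protocol BCB114". Criterion 5 of Protocol 4.2 admits patients treated with diet and exercise alone or "in combination with a stable dose of an oral antidiabetic agent (eg, metformin and/or SU) and/or insulin". Nothing in Protocol 4.3 excludes SU users.

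Appendix F 7.3 lists what substudy patients should not receive in the off-drug period after Week 52: "Insulin secretagogues (e.g., meglitinide, nateglinide, and sulfonylureas), DPP-4 inhibitors, or GLP-1 receptor agonists (e.g., exenatide and liraglutide". It does not say how or when a patient already on SU comes off it.

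The Protocol synopsis (Study Design and Methods) and Section 6.2.1 have patients take their usual concomitant antidiabetic treatment at about the same time each day for the whole study. Section 3.2 counts the 10-week post-treatment follow-up as part of the study. Section 5.6 adds "Dosages for certain concomitant medications should be maintained constant during the study (Section 4.2", with an exception where the investigator or a treating physician instructs otherwise.

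The substudy's primary endpoint (Appendix F 12.2.1) is the change in C-peptide incremental AUC(0-240) from Week 0 to Week 52 and to Week 62. Appendix F 12.3.2 planned paired t-tests. SAP Section 5 withdraws the formal analysis because too few data were collected. SAP 4.2.5 keeps summaries of observed values and change from baseline, with a patient listing, and makes no split by SU use. The evaluable set (Appendix F 12.1, SAP 2.1.7) requires compliance with both the main protocol and the substudy.

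**The concern.** Appendix F 7.3 itself classes SU as an insulin secretagogue, and the substudy measures C-peptide secretion. Changing SU status between two tests therefore changes something that acts directly on the endpoint. The comparison is within patient, so no control arm cancels it.

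Appendix F deals with background insulin for some endpoints: HOMA and the insulinogenic index are limited in 12.2.2 to patients not taking insulin. It has no matching provision for SU, and the C-peptide endpoint carries no restriction at all.

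What is at stake is the Week 62 result. It is there to show whether any beta-cell effect outlasts EQW. A fall caused by loss of SU could be read as loss of the EQW effect.

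**Working it through.** **1. Which barred class can be background treatment?** Set Appendix F 7.3 beside the main entry criteria.

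| Class barred by 7.3 | Status at entry |
|---|---|
| Sulfonylurea | Admitted at a stable dose (4.2, criterion 5); no exclusion |
| Meglitinide, nateglinide | Limited by 4.3, 10(e): "Alpha-glucosidase inhibitors, meglitinide, nateglinide, or pramlintide for >1 week in the 1 month prior to Visit 1 (Screening" |
| DPP-4 inhibitor | Excluded by 4.3, 10(f): "DPP-4 inhibitors within 30 days prior to Visit 1 (Screening" |
| GLP-1 receptor agonist | Any earlier use excluded (4.3, criterion 7) |

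SU is the only barred class that entry expressly allows.

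**2. What is each patient taking at each meal test?** Week 0 testing comes before the first dose (Appendix F 9.1.1; SAP 1.4.4 also has a Week 0 sample). Let R be the part of the Week 0 to Week 62 change not due to SU, and s the drop in incremental AUC from losing SU.

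| Patient | Week 0 | Week 52 | Week 62 | Week 0 to 62 change |
|---|---|---|---|---|
| No background SU | neither | EQW | neither | R |
| SU, follows 7.3 | SU | SU + EQW | neither | R - s |
| SU, continues | SU | SU + EQW | SU (breach of 7.3) | R, but evaluability in doubt |

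SU is present at both ends of the Week 0 to Week 52 change, so that change is unaffected. The middle row carries the confounding. The last row raises the question of who belongs in the Week 62 summary.

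**3. The plan's own figure.** Appendix F 12.4 gives about 93% power for n = 20, change 90, SD 110, alpha 0.05. For a paired t-test, df = 19 and the noncentrality is 90/110 x sqrt(20) = 3.66. Two-sided power is 0.93430, the tabulated value; all 12 rows of the table reproduce. The figure is not in dispute, and 90 and 110 serve below only as a scale.

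**4. Size.** With k SU users following 7.3 among n patients, the mean Week 62 change shifts by (k/n) x s. The documents give neither k nor s. Assumed here: n = 20, k from 0 to 4, s from 30 to 90 nmol*min/L.

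| k of 20 | Shift at s = 30 | Shift at s = 90 |
|---|---|---|
| 0 | 0 | 0 |
| 1 | 1.5 | 4.5 |
| 2 | 3 | 9 |
| 4 | 6 | 18 |

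The planned standard error of the mean change is 110/sqrt(20) = 24.6, so for k of 1 to 4 the shift is 1.5/24.6 = 0.06 to 18/24.6 = 0.73 standard errors. If fewer than 20 patients contribute, as SAP Section 5 suggests, each SU user weighs more, because the weight is k/n.

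**5. Precision if SU users are shown separately.** With 18 patients left the standard error is 110/sqrt(18) = 25.9; with 16 it is 110/sqrt(16) = 27.5. Power for the planned test would have been 0.905 and 0.864, but that test is no longer to be run.

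**The case against.** The strongest reply is that little rests on Week 62. The substudy is exploratory and voluntary, the SAP has dropped the paired t-test, and the trial's primary and secondary endpoints do not depend on it. That stands, and it limits the point to interpretation of a descriptive summary.

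A second reply is that the evaluable set already deals with SU users, and that Appendix F 12.1 lets its definition be refined before database lock. This is partly right. A patient who continues SU breaches 7.3 and may be left out. But one who complies by stopping is not clearly removed, and that is the patient whose change is confounded.

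Some stronger readings are tempting, and the documents do not support them:

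- *Section 5.6 forbids stopping SU.* It allows changes on instruction. The tension with 7.3 comes from the synopsis and Section 6.2.1.
- *Patients must stop SU at the moment EQW stops.* Section 7.3 says they should not be treated with it and gives no procedure or timing. Stopping is an inference, though no other course complies for a patient still on SU.
- *A known share of the substudy is affected.* No SU rate is given, and nothing shows that any substudy patient takes SU.
- *The substudy creates a gap in oversight.* No visit or call is scheduled between Weeks 52 and 62 for any patient in the trial, so the gap is not particular to the substudy.

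**Conclusion.** The contradiction is real and stands in the current text: a patient can qualify on SU, be told to keep usual treatment for the whole study, and be barred from SU for its last 10 to 12 weeks. If a background SU user follows 7.3, the Week 0 to Week 62 C-peptide change cannot be attributed to EQW alone.

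The consequence is modest. Under the assumptions above the shift in the mean is 1.5 to 18 nmol*min/L for 1 to 4 SU users, and zero if there are none. The direction, towards hiding a lasting effect, assumes that losing SU lowers meal-stimulated C-peptide. The calculation also assumes that users stayed on SU through Week 52 and that meal tests ran at Week 0 as scheduled. A reader might infer that the substudy's conclusion on durability fails. The documents do not support that, because the SAP plans no inference at Week 62.

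**What to change.** **Protocol.** Reconcile Appendix F 7.1, 7.2 and 7.3 with Protocol 4.2, 5.6, 6.2.1 and the synopsis, so that it is clear how a background SU user is to be handled in the off-drug period. Which medication rule applies is for the sponsor's clinicians.

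**SAP 4.2.5.** Summarize the Week 62 change for patients without background SU, show background SU users separately, and flag SU use at Weeks 0, 52 and 62 in the listing. State how SU users who continued are treated under the evaluable-set definition in SAP 2.1.7.

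A filter that keeps only patients with the same secretagogue use at Weeks 0 and 62 would be a poor substitute. It would retain a patient who breached 7.3 and drop one who complied, against the compliance-based evaluable set.

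**Cost.** A clarification in Appendix F, a short addition to SAP 4.2.5, and a smaller n in the main Week 62 summary. Little new derivation is needed: SAP 4.2.1.4 already classifies medications by start and stop date, including those started after treatment, and SAP 4.2.4.7 already groups patients by baseline SU use.
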